618 hours to warm- up and provide CGM values. The first 12 hours of CSII to MDI transition
619 is crucial for primary outcomes.

620 ▪ Instructions to use Dexcom G6

621 Insulin pump and pump related supplies would be patients own. Similarly, patients will use their
622 own blood glucose meter for SMBG.

623 **12.2. Packaging and labelling of study medication(s)**

624 All the subjects will be provided sufficient study products including insulin pens, and pen needles.

625 Direction of use of insulin pen will be provided as outlines in the protocol.

626 Documentation of the study drugs/devices will be documented for each subject in accordance with
627 drug and device standard operating procedure of the Barbara Davis Center for Diabetes and the
628 University of Colorado Denver.

629 **12.3. Storage and drug accountability of study medication(s)**

630 The drug (Insulin degludec and Aspart) will be stored according to approved label. The
631 temperature log will be monitored at the site and any temperature fluctuation will be reported as
632 deviation.

633 Subjects will be provided educational material(s) on direction of use of insulin and the storage.

634 Subjects will be instructed to store insulin in outer carton to protect from the light and cap should
635 be kept on the pen when not in use. Each insulin pump should be used within 26 days from the day
636 of opening.

637 CGM (sensor and transmitters) will be stored per manufacturer' recommendation.

638 **12.4. Auxiliary supply**

639 The following will be supplied to study participants for the duration of clinical trial;

640 Needles for insulin pen, lancets, instruction for the use of insulin pens, instruction of CGM use and
641 calibration.

642 **13. CONCOMITANT ILLNESS(ES) AND MEDICATION(S)**

643 Concomitant illness is any illness that is present at the start of the trial (*i.e. at the first visit*). For
644 each concomitant illness, date of onset, date of resolution or continuing, at a minimum, should be
645 recorded.

646 Concomitant medication is any medication other than the trial product(s) that are consumed during
647 the trial, including the screening and run-in periods. The information collected for each
648 concomitant medication includes, at a minimum, dosage, start date, stop date or continuing, and
649 indication.

650 Details of all concomitant illnesses and medication will be recorded at trial entry (*i.e. at the first*
651 *visit*). Any changes in concomitant medication must be recorded at Visit 6 at the time of
652 randomization. If the change influences the subject's eligibility to continue in the trial, the
653 investigator may withdraw the subject from the clinical trial.

654 **14. ADVERSE EVENTS:**

655 An adverse event (AE) is any untoward medical occurrence associated with the use of a drug in
656 humans, whether considered drug related or not. AE can be unfavorable symptoms, sign
657 (abnormality on physical exam or laboratory findings) or disease temporarily associated with the
658 use of products whether or not related to the products.

659 Few examples (but not limited) of AEs are clinically significant worsening of concomitant illness,
660 a new illness, clinically significant radiological or laboratory abnormalities suggesting a disease or
661 organ toxicity.

662 The following three definitions are used when assessing an AE:

663 • **Severity assessment**

664 ▪ **Mild** - no or transient symptoms, no interference with the subject's daily activities.

665 ▪ **Moderate** - marked symptoms, moderate interference with the subject's daily
666 activities.

667 ▪ **Severe** - considerable interference with the subject's daily activities; unacceptable.

668 • **Causality assessment**

669 The following terms are used when assessing the relationship between an AE and the
670 relevant study product(s):

671 ▪ **Probable** - Good reason and sufficient documentation to assume a causal
672 relationship.

673 ▪ **Possible** - A causal relationship is conceivable and cannot be dismissed.

674 ▪ **Unlikely** - The event is most likely related to etiology other than the study product.

675 • **Final outcome of an AE**

676 ▪ **Recovered/resolved** - The subject has fully recovered, or by medical or surgical
677 treatment, the condition has returned to the level observed at the first trial-related
678 activity after the subject signed the informed consent.
679

- 680 ▪ **Recovering/resolving** - The condition is improving and the subject is expected to
681 recover from the event. This term is only applicable if the subject has completed the
682 trial or has died from another AE.
- 683 ▪ **Recovered/resolved with sequelae** - The subject has recovered from the condition,
684 but with lasting effect due to a disease, injury, treatment or procedure. If a sequela
685 meets an SAE criterion, the AE must be reported as an SAE.
- 686 ▪ **Not recovered/not resolved** - The condition of the subject has not improved and
687 the symptoms are unchanged, or the outcome is not known.
- 688 ▪ **Fatal** - This term is only applicable if the subject died from a condition related to
689 the reported AE. Outcomes of other reported AEs in a subject before he/she died
690 should be assessed as "recovered/resolved", "recovering/resolving",
691 "recovered/resolved with sequelae" or "not recovered/not resolved". An AE with
692 fatal outcome must be reported as an SAE.
- 693 ▪ **Unknown** - This term is only applicable if the subject is lost to follow-up.

694 Serious adverse event

695 An adverse event or suspected adverse reaction is considered "serious" if, in the view of the
696 investigator, it results in any of the following outcomes:

- 697 ▪ Results in death, or,
698 ▪ Is life-threatening, or,
699 ▪ Requires inpatient hospitalization or prolongation of existing hospitalization, or,
700 ▪ Results in persistent or significant disability/incapacity, or,
701 ▪ Is a congenital anomaly/birth defect,

702 ▪ Is a medically important event that may not result in death, be life threatening or require
703 hospitalization may be considered an SAE when - based on appropriate medical judgement
704 -they may jeopardize the subject and may require medical or surgical intervention to
705 prevent one of the outcomes listed in the definition of SAE

706 Suspected transmission of an infectious agent should be considered as an SAE.

707 Non-serious AE

708 Any AE that does not fulfill the definition of SAE.

709 Medical event of special interest (MESI)

710 A MESI is an event which, in the evaluation of safety, has a special focus. A MESI is an AE (SAE
711 or non-serious AE) which fulfils one or more of the below defined MESI criteria.

712 ▪ Medication errors concerning trial products:

713 – Administration of wrong drug

714 – Wrong route of administration, such as intramuscular instead of subcutaneous

715 – Accidental administration of a lower or higher dose than intended, however the

716 administered dose must deviate from the intended dose to an extent where clinical

717 consequences for the trial subject were likely to happen as judged by the investigator,

718 although not necessarily did happen.

719 Overdose and missed insulin injection resulting in severe hypoglycemia or hyperglycemia are
720 considered as AE or SAE depending on severity.

721 Suspected Unexpected Serious Adverse Reactions (SUSAR)

722 An unexpected adverse reaction (UAR) is an adverse reaction that is not consistent with the

723 product information in the summary of product characteristics (SPC, i.e.US prescribing

724 information). The current version or any updated if available during the clinical trial for US
725 prescribing information for study drugs will be used as SPC. If UAR is severe enough to define as
726 SAE is called as SUSAR.

727 Technical complaint

728 A technical complaint is any written, electronic, or oral communication that alleges product
729 (medicine or device) defects. The technical complaint may be associated with an AE, but does not
730 concern the AE itself.

731 Reportable Device Issues

732 AE and Unexpected Adverse Device Events (UADE) arising from the use of blinded CGM
733 (Dexcom G6) will be reported irrespective of severity, except in following circumstances:

734 The following device issues are anticipated and will not be reported unless the criteria for AE
735 reporting described above are met

- 736 • Component disconnections
- 737 • CGM sensors lasting fewer than 7 days
- 738 • CGM tape adherence issues
- 739 • Battery lifespan deficiency due to inadequate charging or extensive wireless
740 communication
- 741 • Intermittent device component disconnections/communication failures not leading to
742 system replacement
- 743 • Device issues clearly addressed in the user guide manual that do not require additional
744 troubleshooting
- 745 • Skin reactions from CGM sensor placement that don't meet criteria for AE reporting

746

747 **Safety Monitoring Officer**

748 A safety-monitoring officer ([name]) will independently monitor the study, including
749 adverse events and study drug or device issues with potential to impact participant safety. A
750 monthly meeting will be held between study team and the safety officer to review any adverse
751 events. Following each safety review, a summary recommendation from the safety monitoring
752 officer will be collected.

753 Reporting and follow-up of adverse events

754

755 All events meeting the definition of an AE must be collected and reported. This includes events
756 from the first trial-related activity after the subject has signed the informed consent until the end of
757 the post-treatment follow-up period.

758 During each contact, the trained professional research associate will ask the subject about AEs and
759 technical complaints, for example by asking: "Have you experienced any problems since the last
760 contact?". All AEs will be recorded by the investigator on an AE form. SAE will be recorded
761 within 24 hours of the investigator's first knowledge of the SAE.

762 The investigator is responsible for reporting all AE to COMIRB within five business days per the
763 University of Colorado Denver policy

764 (<http://www.ucdenver.edu/research/Research%20Administration%20Documents/Unanticipated-Problem-Reporting-Policy.doc>).

765 All non-severe and severe AE will be followed by till the end of the study
766 and will be reported to the COMIRB.

767 If a subject becomes pregnant during the study, the subject will be dropped from the study and
768 followed until the pregnancy outcomes. Pregnancy will be reported as AE (or SAE if fulfills the

769 criteria of SAE) and it will be reported to the study sponsor (NovoNordisk). Pregnancy
770 complications will be recorded as adverse events and if the infant has a congenital abnormality or
771 birth defect, it will be reported and notified to the COMIRB and the sponsor.

772 All SAE and SUSAR will be reported to NovoNordisk within 15 days from the investigator
773 becoming aware of such adverse events. The following information will be provided to the
774 sponsor; study name, patient identification (e.g. initials, sex, age), event (preferably a diagnosis),
775 drug name, reporter identification (e.g. Name, or initials), causality, and outcome.

776 **14.1. Precautions/over-dosage**

777 Insulin over or under dose can cause severe hypoglycemia or hypoglycemia. All subjects will be
778 explained on the insulin dose and instructed on insulin pen use as a precautionary measures. The
779 education on recognition of hypoglycemia or hyperglycemia and its treatment will be provided at
780 screening and as needed during the study.

781 **14.2 Risks and Discomforts**

782 a) Blood Drawing Risks

783 The risks of drawing blood from a vein include temporary discomfort from the needle stick
784 (common), bruising (common), excessive bleeding (unlikely), lightheadedness (rare), infection
785 (rare), and fainting (rare).

786 b) Fingertick Risks (for A1c and finger stick glucose monitoring)

787 It may hurt when the lancet goes into a participant's finger but not for long. In about 1 in 10 cases,
788 a small amount of bleeding under the skin will produce a bruise. A small scar may persist for
789 several weeks. The risk of an infection is less than 1 in 1,000 people.

790 c) Related to CGM

791 Wearing sensors can cause adverse skin reactions such as pain at the site sensor insertion. The
792 adhesive pads may cause skin erythema for 1 to 2 days or more. An allergic reaction to 1 or more
793 parts of CGM devices may occur which can be mild, moderate, or severe (rare). In rare cases, an
794 infection at the sensor site may occur. In rare cases, the sensor or needle may break inside the body
795 and would require a minor surgical procedure to remove it. We will also screen out individuals
796 with a history of serious skin reactions to adhesives.

797 d) Risk of Hypoglycemia (Low Blood Sugar)

798 As with any person with diabetes who uses insulin, there is always a risk of having low blood
799 sugar (hypoglycemia). Symptoms of low blood sugar can include sweating, jitteriness, and not
800 feeling well. There is also the possibility of fainting or seizures (convulsions), brain damage, or
801 death with a very low blood sugar. Since we will be closely monitoring participants during this
802 study, a serious low blood sugar is less likely to occur in any study participant. Even if a low blood
803 sugar does occur, it usually goes away quickly with treatment (carbohydrates) that raises the blood
804 sugar. A severe low blood sugar may require that a participant get an injection of glucagon and/or
805 have emergency services to help raise his/her blood glucose level.

806 e) Risk of Hyperglycemia (High Blood Sugar)

807 Hyperglycemia usually does not cause many obvious symptoms, but participants may become
808 thirsty, fatigued, or have a higher level of sugar in their urine. In severe cases of hyperglycemia,
809 diabetic ketoacidosis (DKA) or coma may occur. Hyperglycemia leading to DKA can lead to renal
810 failure (kidney failure), cardiac arrhythmia (irregular heartbeat), myocardial infarction (heart
811 attack), rhabdomyolysis (muscle breakdown), and even death. A serious effect from

812 hyperglycemia is not expected to occur in any study participant, as we will be monitoring blood
813 glucose levels frequently.

814 f) Psychosocial Questionnaires

815 Answering questionnaires about thoughts, concerns, and distress related to diabetes and general
816 quality of life assessments may result in undesired thought processes and/or emotions. These
817 feelings may be transitory, recurrent, or permanent though most risks are minimal/transitory.

818 g) Unknown Risks

819 In any study, there may be additional risks that we do not know about at this time. This is not
820 likely but is always a possibility. If we become aware of any new risks, participants will be told
821 about them. They will be able to decide if they want to continue to participate in this study. If a
822 treatment or procedure has increased risks because it was not done according to study procedures
823 due to error, participants will be informed, and the necessary steps will be taken to care for them.

824 h) Confidentiality

825 There is a risk of a breach in confidentiality. Thus, a confidential subject database will be
826 established to maintain study data. Data will be entered into REDCap (Research Electronic Data
827 Capture). REDCap is an internal secure, computerized database system at the University of
828 Colorado Denver. This system allows data entry, survey/questionnaire building, data exportation
829 to statistical packages, and is HIPAA compliant. Each subject will be assigned an identification
830 number, which will be used to code and identify all of that subject's records. This will avoid the
831 continual use of subject names. REDCap surveys can be sent to study participants via e-mail for
832 direct input into the database. All study data will be locked in the PIs' offices and all relevant
833 computer study files will be input on staff computers, which are password protected and contain

834 encryption software. Data storage will be on a secured server maintained by the University of
835 Colorado. The server is backed up nightly and a copy of the back-up file is kept off site in a secure
836 facility. Data access will be limited to study personnel. Study results may be presented in the form
837 of posters, abstracts, oral presentations, or publications at academic meetings or in journals. In all
838 forms of study result reporting, subject identification will not be disclosed. A study subject may
839 access his/her protected health information at any time by requesting said information in writing of
840 the investigator. The investigative team has been trained in IRB and HIPAA compliance issues
841 and will maintain confidentiality and protect health information. The above-stated procedures have
842 been highly effective in preventing breaches of patient confidentiality for the prior and current
843 research studies in which the PI has been and continues to be involved.

844

845 **15. PUBLICATION PLAN:**

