270 anticipated change in physical activities or diet at the discretion of the investigators.
271
272

273 **5.3. Withdrawal criteria**

- 274 • Participation in this research is voluntary. Subjects may withdraw at will at any time. When
275 withdrawing from the study, the participant should let the research team know that he/she
276 wishes to withdraw. A participant may provide the research team with the reason(s) for
277 leaving the study, but is not required to provide their reason.
- 278 • Participants will be withdrawn from the study if they become pregnant, actively try to
279 become pregnant, develop an allergic reaction to insulin/adhesives, severe episodes of
280 hypoglycemia/hyperglycemia, or at the judgement of investigators due to safety concerns,
281 such as abnormality in laboratory exam results.
- 282 • After withdrawal, the participant will be given instructions on how to safely stop using
283 study medications and, eventually, on how to correctly and safely return to the previous
284 insulin regimen. Instructions are also given on who to contact if there are any questions or
285 concerns that arise after study withdrawal.
- 286 • At the time of withdrawal, the research participant should let the research team know if
287 he/she will allow the use of his/her health information and collected data by the researchers.

288 **5.4. Subject replacement**

289 Subject replacement will occur only if withdrawal occurs before the one-week randomization
290 phase. Subjects will not be replaced during the one-week randomized phase.

291 **5.5. Rationale for study population**

292 In anticipation of screening failure or withdrawal or anticipated issues due to covid-19 pandemic,
293 we plan to screen up to 40 subjects to have 30 complete the clinical trial.

294

295

296 **6. VISIT PROCEDURES:**

297 **6.1. Visit 1, week 0, day0, screening and blinded CGM insertion**

- 298 ▪ Subjects will attend a screening visit (Visit 1, week 0) in order to assess eligibility for the
299 study.
- 300 ▪ Before screening takes place, subjects will be provided with written information about the
301 trial and the procedures involved. Subjects will be fully informed, both orally and in
302 writing, about their responsibilities and rights while participating in the trial, as well as
303 about possible advantages and disadvantages when participating in this trial. Subjects will
304 have the opportunity to ask questions and have ample time to consider participation. The

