423 one unit of rapid acting insulin will drop blood glucose. For example; a patient with
424 carbohydrate ratio of 1:15 and correction factor of 1:50 >150 will take 3 units if preprandial
425 blood glucose is ~200 mg/dl for 30 grams of meal (2 units for 30 grams of carbs + 1 unit for
426 correction). Subjects randomized to group 2 will be instructed to start insulin aspart 48 hours
427 after randomization; i.e. when they disconnect their insulin pump.
- 428 ▪ It is likely that patients randomized to standard-of-care group may experience
429 hyperglycemia during first 48-72 hours. Therefore, both groups will be given a diary
430 (**Appendix 1**) to record any correction made during the randomization phase to count extra
431 insulin injections needed to correct blood glucose during first 72 hours.

432 **6.4. Phone call 1 [P1, week 2, visit 2+24hrs] and phone call 2 [P2, week 2, P1+24hrs]**

- 433 ▪ As a safety measures, there will be 2 phone calls 24 and 48 hours after randomization,
434 respectively.
- 435 ▪ Phone call 1 (P1) will be done 24 hours (± 6 hours in case if patient does not respond to first
436 phone call) after visit 2.
- 437 ▪ Phone call 2 (P2) will be done 24 hours (± 6 hours in case if patient does not respond to first
438 phone call) after P1.
- 439 ▪ All subjects will be asked/assessed for

- 440 ○ Any episodes of severe hyperglycemia requiring hospitalization or hypoglycemia
- 441 requiring third person' assistance. These events will be recorded as SAE and insulin
- 442 dose modification will be done at discretion of the investigator for safety reasons.
- 443 ○ Correct insulin dose and administration will be reassessed.
- 444 ○ Maintenance of glucose and insulin injection dairy.
- 445 ○ Any skin reaction at CGM site.
- 446 ■ For Group 2 (overlap transition):
- 447 ○ Instructions to change in basal rate (75% basal reduction) will be done at P1
- 448 ○ Instructions for CSII discontinuation and initiation of insulin aspart based on
- 449 carbohydrate ratio and correction factor at P2

450 **6.5. Visit 3, week 2, day 14±1: end of treatment**

- 451 ■ Blood glucose meter download and review of SMBG.
- 452 ■ Subject's blinded CGM will be removed and downloaded.
- 453 ■ Look for any local skin reaction at the site of CGM insertion.
- 454 ■ Subjects will return all the remained study-related products (CGM device components,
- 455 insulin degludec and aspart pens, and any auxiliary supplies)
- 456 ■ Report any AE/SAE if any.

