491 **6.8. Assessments for Safety:**

492 The following safety assessments will be performed;

- 493 ▪ Time spent in CGM measured hypoglycemia (< 70 mg/dl) and time spent in hyperglycemia
- 494 (≥250 mg/dl)
- 495 ▪ AE/SAE
- 496 ▪ Documented hypoglycemic episodes
- 497 ▪ Height, weight, vitals and physical examination
- 498 ▪ Baseline laboratory assessment
- 499 ▪ Hypoglycemia unawareness assessment (using GOLD questionnaire)
- 500 ▪ Pregnancy test at screening

501 **6.9. Assessments for Efficacy:**

502 The assessment for efficacy is time spent in CGM glucose time-in-range (min/ 24 hours, 70-180
503 mg/dl) during the 7 days of randomization period.

504 **7. EVALUABILITY OF SUBJECTS:**

505 The data for a subject with minimum of 5 out of 7 days of blinded CGM prior to randomization
506 and 5 out of 7 days of blinded CGM after randomization will be evaluable and included for the
507 analysis of primary and secondary objectives.

508 **8. STATISTICAL CONSIDERATIONS:**

509 **8.1. Sample size calculation**

510 In a study by Garg and colleagues, the subjects with T1D on MDI and blinded CGM for first 4
511 weeks of the study spent average of 8.8 hours/day (~528 min/ 24 hours) in CGM defined glucose
512 above 180 mg/dl [21]. Similarly, in the recently published DIAMOND study, subjects on MDI
513 using CGM experienced average of 601 minutes (~10 hours/ day, IQR; 467-793 min) per 24 hours

514 of time spent in hyperglycemia [22]. We assume that subjects in standard of care group would
515 have more hyperglycemia than subjects in overlap transition group. Therefore, the expected CGM
516 hyperglycemia is ~ 650 minutes/24 hours in standard of care and ~ 500 minutes/24 hours in
517 overlap transition group with the differences in CGM glucose by 150 minutes/day between the
518 groups.

519 This study is powered based on the primary endpoint, which is time spent in CGM-measured
520 glucose levels >180mg/dl (hyperglycemia). We have based the sample size on minimal relevant
521 differences between the two treatment groups, using a Type I error rate of 5% and a Type II error
522 rate of 20%. We hypothesize that the primary endpoint, time in minutes spent with glucose levels
523 >180 mg/dl, will be higher in the standard treatment group than in the experimental group (overlap
524 transition group), but we will use a two-sided test to assess differences in hyperglycemia by
525 treatment group. We hypothesize a standard deviation (SD) for time spent in hyperglycemia of

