552 univariate differences between the standard care group and the experimental group for each of the
553 outcomes. Secondary endpoints include time in range (70-180 mg/dl), time spent hypoglycemic
554 (<70 mg/dl), frequency of severe hypoglycemia, number of correction boluses, and patient
555 reported outcomes as defined on the page 7 of the protocol. Secondary endpoints will be
556 examined using student's t-test to compare these outcomes univariately between the standard care
557 and experimental groups. In a sensitivity analysis, CGM metrics will be evaluated in the first 72
558 hours vs entire 1 week as we expect that differences in hyperglycemia and time-in-range will be
559 more pronounced between the two groups in the first 72 hours. For both primary and secondary
560 endpoints, linear regression analysis will be used to examine outcomes by treatment group while
561 adjusting for potential residual confounders, such as age and sex, which may not be fully
562 addressed by randomization. All testing will be two-sided. The analysis will be conducted as an
563 intention-to-treat analysis.

564 **9. DATA HANDLING AND RECORD KEEPING:**

- 565 ▪ All data generated during the study will be retained by the investigator. Safety events will
566 be reported to Colorado Multiple Institutional Review Board (COMIRB) in a timely
567 manner as described under "Adverse Events".
- 568 ▪ Data management is the responsibility of the investigator. All paper and electronic data
569 will be saved in a de-identifiable manner. The data will be stored on BDC computers
570 which are secured by the University of Colorado servers. The data will be accessible only

571 by the study team and if transfer of data needed, appropriate measures, including
572 encryption of data files will be used to ensure security and subject confidentiality.

- 573 ■ The records will be stored securely and kept for minimum of 10 years per the Standards
574 Operating Procedures (SOP) of the University of Colorado [23].
575 [[http://www.ucdenver.edu/research/Research%20Administration%20Documents/COMIRB
-Policy-and-Procedures-Document.pdf](http://www.ucdenver.edu/research/Research%20Administration%20Documents/COMIRB
576 -Policy-and-Procedures-Document.pdf)]

577 **10. ETHICS:**

- 578 ■ The trial will be conducted in compliance with this protocol, ICH GCP, the University of
579 Colorado COMIRB research policy and in accordance with the Declaration of Helsinki
580 [23-25].

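### The 5-of-7-day CGM rule in Section 7 drops randomized participants because of post-randomization events, so the primary analysis is not the intention-to-treat analysis that Section 8.2 states

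*Combined protocol and SAP*

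**What the plan says.** **Section 7** makes a participant's data usable only with 5 of 7 CGM days before randomization "and 5 out of 7 days of blinded CGM after randomization will be evaluable and included for the" analysis of primary and secondary objectives.

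**Section 8.2** ends: "All testing will be two-sided. The analysis will be conducted as an" intention-to-treat analysis. Its one sensitivity analysis compares the first 72 "hours vs entire 1 week as we expect that differences in hyperglycemia and time-in-range will be" larger early on. It names no other analysis set.

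**Section 5.3** lists reasons for leaving the study as a whole, not only the regimen. The list starts "Participants will be withdrawn from the study if they become pregnant, actively try to", then covers allergic reaction to insulin or adhesive and severe episodes of "hypoglycemia/hyperglycemia, or at the judgement of investigators due to safety concerns". At withdrawal the participant says whether "he/she will allow the use of his/her health information and collected data by the researchers".

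**Section 5.4** adds: "Subjects will not be replaced during the one-week randomized phase".

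**Section 6.5** (Visit 3) has the only scheduled CGM download after randomization: the "blinded CGM will be removed and downloaded" there. No section describes CGM continuing after withdrawal.

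**Section 6.4** has severe events found at the two safety calls recorded as SAEs, with insulin dose modification at the investigator's discretion. It does not mention withdrawal.

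**The concern.** Whether a randomized participant is analysed depends on what happens after randomization. An exit under 5.3 before five CGM days, or a sensor that stops early (Section 14 anticipates sensors lasting under 7 days), takes the person out of every primary and secondary comparison. The reason for exit may be related to the outcome, because severe hyperglycemia and severe hypoglycemia are both exit reasons. The plan defines no modified analysis set and no missing-data method. Two analysts could therefore follow Section 7 or Section 8.2 and reach different primary results.

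Read literally, the rule has two further effects:

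- **Secondary endpoint 3.** The severe event that caused an early exit is not counted in the endpoint that measures severe events.
- **The 72-hour analysis.** A participant who leaves after day 3 with a complete first 72 hours is dropped from the analysis of exactly that window.

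**Working it through.** **1. The plan's own figure.** Two-sample t-test, 15 per arm, SD 140, two-sided 5%, difference 148.4 min: the noncentral t distribution with 28 degrees of freedom gives 80.0% power, as stated in 8.1. The sample size is not in question. With the planned means of 650 and 500 the difference is 150 and power is 81%. The standard error of the difference is 140 × √(2/15) = 51.1 min.

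**2. Tracing one exit.** A participant leaves on day 2 or 3 and allows use of the data. Section 7 requires 5 days, so the data are not analysed. Section 5.4 bars replacement. The 72-hour analysis names no different set. Section 8.2 nevertheless describes the result as intention-to-treat.

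**3. Size of one loss.** From the plan: means, SD, 15 per arm. Assumed, because the documents give no such figures: exit after d = 2 or 3 days; p = 500 to 650 min/day above 180 mg/dl after return to the pump; correlation r between exit and time above 180. At r = +1 the exiter is the highest of the 15 in that arm, at r = −1 the lowest. The expected largest of 15 standard normal values is 1.736.

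- Exiter's expected value: own = arm mean + r × 140 × 1.736.
- If lost, the arm mean moves by −r × 140 × 1.736 / 14 = −17.4r.
- If followed, the arm mean moves by (v − own)/15, where v = (d × own + (7 − d) × p)/7.

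Example, Group 2 at r = +1: own = 500 + 243 = 743. Lost: 150 + 17.4 = 167.4. Followed with d = 3, p = 650: v = (3 × 743 + 4 × 650)/7 = 689.9, so the arm mean moves by −53.1/15 = −3.5 and the difference is 153.5. Gap: 167.4 − 153.5 = 13.8 before rounding, and 13.8/51.1 = 0.27 standard errors.

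Estimated difference, Group 1 minus Group 2, in min/day:

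| Exit | r | If lost | If followed | Gap (lost − followed) |
|---|---|---|---|---|
| Group 1 | +1 | 132.6 | 131.3 to 140.7 | −8.1 to +1.4 |
| Group 1 | +0.5 | 141.3 | 137.1 to 145.4 | −4.1 to +4.2 |
| Either | 0 | 150.0 | 142.9 to 150.0 | 0 to +7.1 |
| Group 2 | +0.5 | 158.7 | 148.6 to 155.8 | +2.9 to +10.0 |
| Group 2 | +1 | 167.4 | 153.5 to 161.6 | +5.8 to +13.8 |
| Group 2 | −0.5 | 141.3 | 137.1 to 145.4 | −4.1 to +4.2 |
| Group 2 | −1 | 132.6 | 131.3 to 140.7 | −8.1 to +1.4 |

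Negative r represents an exit for hypoglycemia by someone with little time above 180. By symmetry, a Group 1 exit at negative r takes the Group 2 figures at positive r. In simulation, power for one Group 1 exit at r = +0.5 is 75% if lost and 76-80% if followed.

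**4. Partial weeks.** Averaging whatever days exist is not a safe substitute, because it gives the first days too much weight. The check assumed a within-person daily SD of 150, a weekly-mean SD of 140, compound symmetry, and a Group 1 excess of 150 averaged over the week, either even or concentrated early. The Group 1 participant with the worst first 2-3 days contributed only those days. Against a true 150, dropping that person gives 134-136, a plain average of available days gives 153-169, and a day-adjusted model gives about 150.

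**5. Endpoint 3.** One severe event in an early exiter is 1/15 if all randomized are counted and 0/14 if the exiter is dropped. This concerns the denominator only and supports no inference.

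**The case against.** **Few people will be affected.** This stands. Section 3.2 defines severe hypoglycemia as needing external assistance and severe hyperglycemia as needing hospitalization. The randomized phase is one week. Section 5.2 excludes recent severe hypoglycemia, recent DKA, hypoglycemia unawareness and HbA1c above 8.5%, and Section 6.3 screens out poor run-in compliance. A reader might infer that the hyperglycemia expected in Group 1 during the first 48-72 hours would itself trigger withdrawal. It would not, because it does not by itself meet the definition of severe.

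**5.3 is an ordinary safety rule.** This stands too. The defect is in Section 7. A reader might infer that 5.3 removes everyone with a severe episode, but 6.4 provides for dose modification and does not mention withdrawal, so the text does not settle that.

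**Following exiters is a choice of estimand.** Largely right. At r = 0, losing the person gives 150.0 and following gives 142.9-150.0, because days back on the pump dilute the contrast. Longer follow-up does not reliably bring the estimate nearer to 150, so it is offered below only as an option.

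**The severe event is recorded anyway.** It is, as an SAE, and intention-to-treat could be read as keeping it in endpoint 3. One sentence would settle it.

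None of this reconciles Section 7 with Section 8.2.

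**Conclusion.** The point holds as an inconsistency between Sections 7 and 8.2. Whenever someone has fewer than 5 post-randomization CGM days, following the plan gives a comparison that is not the intention-to-treat comparison it states. It should be corrected, mainly because the analysis ought to match its stated principle and the correction is cheap.

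The likely numerical effect is small: at most about 14 min/day (0.27 standard errors) for one exit. This rests on the plan's means and SD, normal data, exit on day 2 or 3, and 500-650 min/day afterwards. The documents give no exit rate.

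A reader might go on to infer a large or predictable bias. Removing the two or three most hyperglycemic Group 1 participants would cut power from 81% to 63% or 52%, but nothing in the documents suggests that many losses or such perfect selection. Nor can the rule be said to favour one strategy: one Group 2 exit moves the estimate by +3 to +10 min/day at r = +0.5 and by −4 to +4 at r = −0.5.

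**What to change.** Amend Sections 7 and 8.2:

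1. **Primary set.** All randomized participants with any post-randomization CGM, in their assigned arm. The 5-of-7-day set becomes a sensitivity analysis.
2. **Partial weeks.** Analyse daily minutes above 180 mg/dl in a repeated-measures model with arm, day and arm-by-day, and average the arm difference over days 1-7. With complete weeks this equals the difference in means that the t-test compares. Do not average the available days.
3. **72-hour analysis.** Include everyone with CGM in that window.
4. **Endpoint 3.** Count events in all randomized participants, whatever their CGM completeness.
5. **No post-randomization CGM.** Report these participants by arm with the reason; they remain missing.

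Optional: in 5.3, separate stopping the regimen from withdrawing consent, and let those who only stop the regimen keep the blinded sensor to Visit 3 if they agree and have no adhesive reaction. Without this step the model treats unrecorded days as resembling those of similar participants in the same arm. With it, days back on the pump are observed and count in the assigned arm. A line in 6.4 saying whether a severe event leads to dose modification or to withdrawal would also help.

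Cost: a protocol amendment with ethics-board approval, and a somewhat more complex model. The optional step also needs consent-form wording and brings some dilution: one Group 1 exit at r = +0.5 would give 137-145 instead of 150. The sensor and Visit 3 are already planned.
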